Sample size: A negative outcome (i.e. %BF) was selected as the primary efficacy end point of this trial. We used our own institutional data to calculate the sample size for this trial and estimated that a 3% absolute difference was clinically meaningful because the average difference between term and preterm infants is 3%.⁶

Follow-up: We estimated that follow-up rates at 3 months of age will be higher than our follow-up rates at 2 years of age for extremely preterm infants (approximately 80% at our institution). Follow-up at 3 months of age to assess infant body composition will allow comparison of our results with reference data in term infants.

Generalizability: Given the pilot nature of this trial, we will focus on minimizing systematic errors in the trial to improve accuracy of our results and increase internal validity. It is expected that the precision of our estimates and the external validity of our results will be affected by our small sample size.

Specific Aim 2 will test the hypothesis that serial assessment of infant body composition slows weight gain following hospital discharge and attenuates health disparities in body fat accrual at 3 months of age.

Overview and preliminary data: Aim 2 will be a secondary analysis of our pilot randomized trial. In a prospective study of body composition, we corroborated that racial/ethnic minorities have higher in-hospital growth rates than white infants (unpublished data).

Inclusion criteria, exclusion criteria, and outcome: Demographic and nutritional data from infants who participated in the pilot trial will be used for this analysis. Infants with missing follow-up data will be excluded. %BF at 3 months of age will be the dependent variable in the primary analysis.

Statistical analysis: In this analysis, race/ethnicity will be entered as a dichotomous variable: white (reference group) and black or Hispanic. To examine the association between weight gain at 2 different time points (before and after hospital discharge) and body fat accrual at 3 months of age within each racial/ethnic group, we will use multivariable regression models. Subsequently, to quantify the degree to which weight gain explains racial/ethnic disparities in body fat accrual, we will employ a decomposition analysis which will help us determine if changes in weight gain after serial monitoring of body fat accrual reduces differences (i.e. observed and predicted) in body fat accrual between minority and white infants⁷.

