HUMAN SUBJECTS

RISKS TO HUMAN SUBJECTS

Human Subjects' Involvement, Characteristics, and Design. This is non-exempt human subjects research.

Characteristics of participants: Our study population will reflect the epidemiology of prematurity in the state of Alabama, with approximately 56% being Black (African-American), 41% White (Non-Hispanic Caucasian), and the remaining 4% Hispanic/Other. This study population has been selected based on the frequency of nutritional problems observed at these gestational ages and the increased risk of adverse health outcomes in this vulnerable population.

Sampling plan, recruitment, and retention. Patients admitted to the neonatal unit of UAB from June 2018 to January 2019 will be screened to determine eligibility for the study. Because the protocol is designed to establish a new hospital-based practice early in life, mothers will be approached by the research staff before eligible very preterm infants reach full enteral feeding.

Sources of Materials

For study participants, data will be collected from electronic medical records. Data containing identifying information will be available only to the PI ([name]) and research personnel directly involved with this study. Information about the study will be shared without individual identifiers. Data will be collected from medical records in accordance with the study protocol. This will include demographic data and other nutrition/feeding data.

Potential Risks

Potential risks: The probability of risk for higher %BF in a patient that participates in this trial is not different than the probability of higher %BF in a patient that does not participate in the trial⁵³. Other theoretical risks of this study are related to clinical decompensation during assessment of infant body composition. They include increased risk of bradycardia or desaturations. Previous studies, including ours (unpublished data), have not reported an association between assessment of infant body composition and any of the above-mentioned risks. Infants may experience some transient discomfort during the PeaPod® assessment which requires them to wear a tight-fitting cap but no other clothing or blanket. Therefore, there are no known risks associated with this trial except loss of confidentiality, as it involves data collection.

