Breach of confidentiality: The main potential risk of this study is breach of confidentiality. This is one of the most common risks of participation in clinical research. Accordingly, our team has designed a strategy to protect participant confidentiality. All participants will be informed of study procedures and gauged for understanding of study tasks. In addition, study personnel will follow regulatory guidelines for obtaining informed consent.

Alternative treatments and procedures: Participants in the intervention and control groups will have full access to all available standard of care clinical services at our neonatal unit, and parents are permitted to withdraw or refuse participation at any time.

Adequacy of Protection against Risks

Recruitment and Informed Consent

Recruitment: When a potential participant is identified, a member of the study will see the parents and/or mother in her room or the baby's room and explain the study. The risks and benefits will be discussed with the parents and time will be given to them to ask questions. It will be made known to them that no treatment will be withheld from their child if they participate in the study.

Informed consent: The research team will attempt to obtain written consent after giving the parents a minimum of 24 hours to think about the study information and ask questions. Randomization will define study group assignment

Study Monitoring Plan. This protocol will be reviewed by the IRB at UAB. Serious adverse events including severe clinical deterioration after assessment of infant body composition will be reported to the principal investigator. Moderate to major complications, defined for the purpose of this trial as events requiring immediate medical attention and/or interventions due to worsening clinical status, will also trigger a notification to the principal investigator. In previous studies that assessed infant body composition in stable preterm

infants, including ours (unpublished data), serious adverse events including bradycardia, desaturations, hypothermia, sepsis, or death were not reported. No interim analyses are planned.

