Protections against Risk. Our team will make every effort to protect all participants' confidential and private information in order to minimize possible study-associated risks. All findings related to any research will be available and provided to study participants in accordance with standard practices. We will also inform all participants that their participation is voluntary, and we will utilize study identification codes in place of personal identifiers on study materials. We will also employ storage and encryption techniques in compliance with UAB Data Security standards to safeguard all electronic data, as well as protections outlined in Subpart C of title 45, part 4 Code of Federal Regulations. All study personnel are required to renew Human Subjects training biannually. No data will be accepted from or distributed to the principal investigator or study staff if regulatory training is not current.

Any provider or caregiver involved in the trial will be able to write to the study coordinator to draw attention to any concern they may have about the possibility of harm arising from the intervention under investigation.

Potential Benefits of the Proposed Research to Human Subjects and Others

Potential benefits of this study are to provide stronger evidence for the safety and efficacy of monitoring body fat accrual as a way of optimizing caloric intake, growth, and fat-free mass in preterm infants. Better quantitative and qualitative outcomes of growth may also be associated with improved long-term neurodevelopmental outcomes.

The potential benefits of this research may include reduction of postnatal growth restriction, reduction in infant morbidity mediated through improved neonatal nutrition, and better growth at time of discharge. Reductions of postnatal growth restriction and improved nutritional parameters could improve long-term neurodevelopmental outcomes of infants. There will be benefit to the medical community in providing additional information on infant body composition in preterm infants.

Importance of the Knowledge to be Gained

As the risk to individual participants is small and potential benefits are significant, the risk/benefit ratio is favorable.

ClinicalTrials.gov Requirements

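### The Potential Risks section finds no known risk beyond confidentiality, yet the intervention acts through feeding and is expected to slow weight gain; inadequate growth is not named as a risk

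*Combined protocol and SAP*

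**What the plan says.** All references are to the combined protocol and SAP.

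- **Potential Risks** considers higher %BF, bradycardia or desaturation around the scan, and discomfort from the cap. It then concludes: "Therefore, there are no known risks associated with this trial except loss of confidentiality, as it involves data collection".
- **Intervention** and the opening of **Specific Aim 1** (Approach) describe what differs between the arms. Both are scanned, but only in the intervention arm do clinicians see the result, with feeding guidelines to act on it. The expected route to lower %BF is a change in diet.
- **Specific Aim 2** (Approach) hypothesises that "serial assessment of infant body composition slows weight gain following hospital discharge".
- **Study Monitoring Plan** sends two kinds of event to the principal investigator: serious adverse events, and moderate to major complications, defined as "events requiring immediate medical attention and/or interventions due to worsening clinical status". It adds: "No interim analyses are planned".
- **Protections against Risk** lets providers and caregivers write to the study coordinator about "any concern they may have about the possibility of harm arising from the intervention under investigation".
- **Potential Benefits** counts growth on the benefit side only: "The potential benefits of this research may include reduction of postnatal growth restriction". The next section concludes: "As the risk to individual participants is small and potential benefits are significant, the risk/benefit ratio is favorable".
- **Recruitment** says of parents: "The risks and benefits will be discussed with the parents and time will be given to them to ask questions".

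**The concern.** Apart from higher %BF, the risk section assesses the measurement, which both arms receive. It does not ask what could go wrong with the part that is randomised, namely feeding changed in response to a body fat report. If that change goes too far, the infant gains too little weight, length or head circumference.

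The plan recognises this trade-off elsewhere. Significance speaks of balancing neurodevelopmental benefit against metabolic risk, the Aim 1 rationale includes preventing growth failure among its goals, and Potential Benefits links better growth to better neurodevelopment.

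Two things are at stake. If the consent discussion follows the risk section, parents hear an incomplete account. And an infant who falters gradually, without an event that needs urgent care or intervention, reaches the investigator only if someone writes in or when outcomes are collected.

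**Working it through.** **1. Mechanism against stated risks.**

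| Element of the plan | Direction of possible harm | Named as a risk? |
|---|---|---|
| Scan (both arms) | Bradycardia, desaturation, discomfort | Yes |
| Data collection (both arms) | Loss of confidentiality | Yes |
| Feeding changed after a report (intervention arm) | Higher %BF | Yes, judged no different from non-participation |
| Feeding changed after a report (intervention arm) | Too little growth | No |

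The last row is the gap. It follows from the plan's own hypotheses and needs no outside evidence.

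**2. Monitoring triggers.** Both triggers depend on a serious or worsening clinical event. Neither refers to weight, length, head circumference, a percentile or a rate of gain. Growth is recorded as secondary outcomes, with no action attached.

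**3. Size of the intended effect on weight.** Inputs: 15% body fat at discharge and a 3-point difference (Sample Size and Power Estimates). Assumptions: fat-free mass is unchanged, and the discharge value is carried to 3 months.

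- Weight ratio = 0.85/0.88 = 0.966, so weight is 3.4% lower.
- If the SD of weight is 12% of the mean (assumed), this is 3.4/12 = 0.28 z. For an SD of 10% to 15% it is 0.34 to 0.23 z.

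The intended effect is small. The risk at issue is overshoot in individual infants, not the average response.

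**4. Can the end-of-trial comparison serve as the safeguard?** (context only) Inputs: 25 per arm, two-sided 0.05, and a base rate of 60% growth failure, which Significance gives for infants of 32 weeks or less. Because that figure includes younger infants than the trial's, 40% is shown as an assumed alternative. Power is by exact binomial enumeration.

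| Change in growth restriction | Fisher | Chi-square |
|---|---|---|
| 60% to 75% | 0.130 | 0.215 |
| 60% to 92% | 0.684 | 0.810 |
| 60% to 95% | 0.822 | 0.907 |
| 40% to 55% | 0.142 | 0.218 |

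The plan also lists continuous growth outcomes, which are more sensitive. On a normal scale, 60% to 75% below a cut-off is a shift of 0.674 − 0.253 = 0.42 SD. A t-test with 25 per arm has power 0.31 for it, and reaches 80% at 0.81 SD (60% to about 86%). That is better than the binary comparison, but still not a per-infant safeguard.

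**5. Why a fixed 1.0 z rule would not work in hospital.** Share flagged = Φ((−1.0 + m)/s), where m is the mean fall in z and s the SD of change (both assumed; s = 0.5).

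- m = 0: Φ(−2) = 0.023, or 0.6 of 25.
- m = 1.0: Φ(0) = 0.5, or 12.5 of 25.

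The count depends almost wholly on the unit's usual early fall in z, so the threshold has to come from unit data.

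**6. Cost to the primary comparison.** The plan's size reproduces first: 2 × (1.960 + 0.842)² × 3.6²/3² = 22.6, so 23 per arm and 46 in total. With 23 per arm, the t distribution gives power 0.789 for a 3-point difference. If 10% of intervention infants were refed and lost the whole effect, the difference would be 3 × 0.90 = 2.7 and power 0.701. At 5% it is 2.85 and 0.747; at 15% it is 2.55 and 0.652.

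**The case against.** The strongest case against has four parts.

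- **The plan questions the premise.** Significance argues that slow gain was wrongly equated with inadequate growth, and cites three randomised trials in which reversing growth failure through rapid gain brought no neurodevelopmental benefit. Aim 2 targets rapid gain, the intervention supplies information to improve nutrition, and the sentence at issue speaks only of known risks. This stands as far as it goes: the documents give no evidence that overshoot occurs. A reader might infer that the trial restricts calories or is likely to cause growth failure, and the documents support neither. But failure to show benefit from rapid gain does not show that too little gain is harmless.
- **Text outside the review may cover growth.** The consent form and feeding guidelines are not in the reviewed text. A reader might infer that parents are never told about growth, or that no growth floor exists; neither can be concluded. What can be said is that the protocol's own risk section is incomplete.
- **Infants are already protected.** Feeding stays with the attending physician, standard care is fully available, routine growth measures continue, and anyone may write in. In hospital this is substantial. It is weaker after discharge, where the slowing is hypothesised, and the attending is also the person the report is meant to influence.
- **The power argument is easily overplayed.** Quoting only the growth-restriction comparison makes the trial look blinder to growth than it is. That is accepted: the power figures are context. Nor is the absence of an interim analysis a fault in a 50-infant pilot, since per-infant review does not depend on one.

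**Conclusion.** The point holds in a limited form. The conclusion that confidentiality is the only known risk is inconsistent with an intervention that acts through feeding and is expected to slow weight gain. Inadequate growth is foreseeable but undemonstrated, and neither the risk account nor the monitoring triggers mention it. This is an error in a stated conclusion, not merely a missing detail, and it should be corrected. It does not undermine the design or the primary analysis.

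The inconsistency rests on the text alone. The weight and z figures rest on assumed SDs and on a discharge %BF applied at 3 months. The power figures rest on a borrowed 60% base rate, with 40% as the alternative. The practical importance of the monitoring addition depends on what the feeding guidelines say.

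**What to change.** **Main change, Potential Risks.** Replace the sentence with:

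> Feeding changes prompted by a body composition report may lead to inadequate gain in weight, length or head circumference; this and loss of confidentiality will be discussed with parents at consent.

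**Secondary and modest, Study Monitoring Plan.** Add:

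> In both arms, growth faltering on routinely recorded anthropometry, by a threshold set from past unit data before enrolment, is notified to the principal investigator for review with the treating clinician; after discharge, weights already in the medical record are checked against the discharge value.

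Do not use a fixed 1.0 z rule in hospital. If the feeding guidelines already contain a growth floor, the monitoring section can simply cite it. The check on recorded weights matters because a rule that acts only at the 3-month visit, the trial's last assessment, comes too late for the interval in which slowing is expected. It reaches only infants whose clinic weights are in the record.

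**Cost.** No new visit or measurement. The notice should carry anthropometry only, so that clinicians of control infants still do not see body composition. If the in-hospital threshold is chosen so that about 1 infant in 10 meets it, expect 0.10 × 25 = 2.5 weight notifications per arm (1.3 to 3.8 at 5% to 15%); adding length and head circumference could at most triple this. Some dilution of the %BF difference is possible. The fall in power from 79% to 70% is a pessimistic case, because it assumes that every flagged intervention infant loses the full effect, whereas the notice prompts review and does not mandate refeeding.
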